5.6 OTHER ASSESSMENTS

5.6.1 Quality of Life Questionnaires DLQI and WLQ

Dermatology Life Quality Index (DLQI) and Work Limitations Questionnaire (WLQ) are questionnaires self-administered by patients at Visits 2, 8 and EOT. DLQI and WLQ will be used to assess quality of life, overall health and disability status, as well as work limitations (see [Appendix 10.6](#) and [10.7](#)).

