6.2.3.1 Early treatment and trial termination

If study medication is discontinued prior to the planned [Flow Chart](#) visit EOT, every effort should be made to have the patient continue in the trial and complete all of the remaining trial visits and procedures including EOT and EOO Visit; with the EOO Visit to be performed 4 weeks after the EOT Visit.

If a patient cannot or will not continue in the trial, the patient should complete EOT Visit procedures instead of the next planned treatment period visit. These patients should be registered as prematurely discontinued in IRT and return to the clinic for End of Observation Visit 16 (± 1) weeks after their last administered dose of BI 655066 (active or placebo). Patients who discontinue from the trial prematurely will not have the option to participate in the open label extension (OLE) study.

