For analysis in each Part (A or B), the Rx Day is calculated relative to the first dose of study drug in the specific study Part. For analysis across Part A and Part B, the Rx days are calculated relative to the date of first dose of study drug injection in Part A.

Definition of Analysis Windows

All time points and corresponding time windows are defined based on Rx Days.

For efficacy analyses, local tolerability, laboratory parameters, and vital sign variables, analysis windows are constructed using the following algorithm:

- Determine the nominal Rx day for each visit (e.g., Week 4 [4 weeks after Baseline visit] equals Rx Day 29).
- In order to include all post baseline data, the first post-baseline interval starts on the first day after the first dose of study drug (Rx Day 2).
- Determine the window around a specific nominal Rx day by adding or subtracting half of the interval between adjacent visits (e.g., days between Week 2 and Week 4 is 14). The threshold between adjacent visits is determined by splitting the interval evenly between the visits. If the resulting split is between Rx days, then the threshold is determined as the midpoint between the adjacent visits. If the resulting split is on an Rx day, then the threshold is determined as being between that Rx day and the Rx day prior to it (e.g., the split between Week 2 and Week 4 would be between Rx Days 22 and 23).
- If more than one assessment is included in a time window the assessment closest to the nominal day will be used. If there are two observations equidistant to the nominal day, the one after the nominal day will be used in analyses. If more than one assessment is included on the same day, then the worst assessment on that day will be used in analyses, except those specified in Section 11.0.

The protocol specified visits and corresponding time windows used in the efficacy analyses, local tolerability, ECG, laboratory parameters, and vital sign variables, are presented in the following tables.

Table 4. Visit Windows for PASI/sPGA and Vital Signs for Part A (ITT_A/PP_A/Safety_A Populations)

Window Label	Target Day	Time Window
Baseline	1	$\leq 1^a$
Week 4	29	[2, 43]
Week 8	57	[44, 71]
Week 12	85	[72, 99]
Week 16	113	[100, 127 ^b]

Rx Day calculated relative to the first dose of study drug. For subjects randomized but not dosed, Rx Day calculated relative to randomization.

- a. If time is collected in vital signs, restrict to records prior to the first dose of study drug.

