- b. The minimum of upper bound and first dose date of study drug on or after Week 16 (and within 105 days of last dose for safety analyses). If time is collected in vital signs, restrict to records prior to the first dose of study drug on or after Week 16.

Table 5. Visit Windows for Laboratory and ECG Parameters for Part A (Safety_A Population)

Window Label	Target Day	Time Window
Baseline	1	≤ 1
Week 4	29	[2, 71]
Week 16	113	[72, 155 ^a]

Rx Day calculated relative to the first dose date of study drug. For subjects randomized but not dosed, Rx Day calculated relative to randomization.

- a. The minimum of upper bound and first dose date/time on or after Week 16 (and within 105 days of last dose for safety analyses).

Table 6. Visit Windows for Other Efficacy Endpoints Only Collected at Week 16 in Part A (ITT_A Population)

Window Label	Target Day	Time Window
Baseline	1	≤ 1
Week 16	113	[2, 225 ^a]

Rx Day calculated relative to the first dose date of study drug. For subjects randomized but not dosed, Rx Day calculated relative to randomization.

- a. The minimum of upper bound and first dose date of study drug on or after Week 16.

Table 7. Visit Windows for Local Tolerability for Part A (Safety_A Population)

Window Label	Target Day	Time Window
Week 1	8	[2,15]
Week 3	22	[16, 25]
Week 4	29	[26, 71]
Week 16	113	[72, 155 ^a]

Rx Day calculated relative to the first dose of study drug. For subjects randomized but not dosed, Rx Day calculated relative to randomization.

- a. The minimum of upper bound and first dose date of study drug on or after Week 16 (and within 105 days of last dose for safety analyses) (and within 105 days of last dose for safety analyses). If time is collected in vital signs, restrict to records prior to the first dose of study drug on or after Week 16.

Table 8. Visit Windows for Analysis of PASI and sPGA in Part B (ITT_B_RR/ITT_B_R/ITT_B_NR/ITT_B_RZB/PP_B_RR Populations)

Window Label	Target Day	Time Window
Entry of B	1	≤ 1
Week 20	29	[2, 43]
Week 24	57	[44, 71]
Week 28	85	[72, 99]
Week 32	113	[100, 127]
Week 36	141	[128, 155]
Week 40	169	[156, 183]
Week 44	197	[184, 211]

Rx Day calculated relative to the first dose of study drug in Part B. For subjects re-randomized but not dosed in Part B, Rx Day calculated relative to the IRT date of re-randomization evaluation.

Table 9. Visit Windows for Laboratory and ECG Parameters for Part B (Safety_B_RR Population)

Window Label	Target Day	Time Window
Entry of B	1	≤ 1
Week 28	85	[2, 141]

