Week 44	197	[142, 211]
Week 48 (EOT + 4 Weeks)	225	[212, 239 ^a]

Rx Day calculated relative to the first dose of study drug in Part B. For subjects re-randomized but not dosed in Part B, Rx Day calculated relative to the IRT date of re-randomization evaluation.

a. The minimum of upper bound and 105 days of last dose for safety analyses.

Table 10. Visit Windows for Vital Signs for Part B (Safety_B_RR Population)

Window Label	Target Day	Time Window
Entry of B	1	≤ 1
Week 20	29	[2, 43]
Week 24	57	[44, 71]
Week 28	85	[72, 99]
Week 32	113	[100, 127]
Week 36	141	[128, 155]
Week 40	169	[156, 183]
Week 44	197	[184, 211]
Week 48 (EOT + 4 Weeks)	225	[212, 239 ^a]

Rx Day calculated relative to the first dose of study drug in Part B. For subjects re-randomized but not dosed in Part B, Rx Day calculated relative to the IRT date of re-randomization.

a. The minimum of upper bound and 105 days of last dose for safety analyses.

Table 11. Visit Windows for Other Efficacy Endpoints Only Collected at Week 44 in Part B (ITT_B_RR/ITT_B_R/ITT_B_NR/ITT_B_RZB/PP_B_RR Populations)

Window Label	Target Day	Time Window
Entry of B	1	≤ 1
Week 44	197	[2, 393]

Rx Day calculated relative to the first dose of study drug in Part B. For subjects re-randomized but not dosed in Part B, Rx Day calculated relative to the IRT date of re-randomization.

Table 12. Visit Windows for Local Tolerability for Part B (Safety_B_RR Population)

Window Label	Target Day	Time Window
Week 28	85	[2, 141]
Week 44	197	[142, 253 ^a]

Rx Day calculated relative to the first dose of study drug in Part B. For subjects re-randomized but not dosed in Part B, Rx Day calculated relative to the IRT date of re-randomization.

a. The minimum of upper bound and 105 days of last dose for safety analyses.

Note. There is no local tolerability at re-randomization and after EOT.

Table 13. Visit Windows for Laboratory and ECG Parameters for ALL_RZB Population

Window Label	Target Day	Time Window
Baseline	1	≤ 1
Week 4	29	[2, 71]
Week 16	113	[72, 155]
Week 28	197	[156, 253]
Week 44	309	[254, 323]
Week 48 (EOT + 4 Weeks)	337	[324, 351 ^a]

Rx Day calculated relative to the first dose of risankizumab.

a. The minimum of upper bound and 105 days of last dose of risankizumab for safety analyses.

Table 14. Visit Windows for Vital Signs for ALL_RZB Population

Window Label	Target Day	Time Window
Baseline	1	$\leq 1^a$
Week 4	29	[2, 43]
Week 8	57	[44, 71]
Week 12	85	[72, 99]
Week 16	113	[100, 127]
Week 20	141	[128, 155]

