10.1.4 Missing Data Imputations

Missing data will be imputed using the following methods for the efficacy analyses:

- Non-Responder Imputation (NRI): the NRI analysis will categorize any subject who has a missing value at a specific visit as a non-responder for that visit. The only exception is when the subject is a responder both before and after this specific visit window, within the same analysis period, then the subject will be categorized as a responder for the visit. The NRI will be the primary approach in the analyses of categorical variables.
- Last Observation Carried Forward (LOCF): The LOCF analyses will use the completed evaluation from the previous visit within the particular analysis period for efficacy measures assessed to impute missing data at later visits in the same analysis period. Baseline efficacy evaluations will not be carried forward. Of note, post-baseline observations from Part A can be carried

forward to the ITT_B_RZB subjects since treatment is the same. LOCF will be the primary approach in the analyses of continuous variables, and the secondary approach in the analyses of categorical variables.

- As-Observed Cases (OC): The as-observed analysis will not impute values for missing evaluations, and thus a subject who does not have an evaluation on a scheduled visit will be excluded from the as-observed analysis for that visit. As-observed analysis will be the secondary approach in the analysis of continuous variables.
- Multiple Imputation (MI): The MI analysis will be used as sensitivity approach to impute missing data in primary and ranked secondary endpoints. The variables to be included in the imputation model are listed below. If MI is not applicable due to the nature of our data (e.g., MCMC algorithm does not converge), logistic regression or mixed effect model repeat measurement (MMRM) methods will be applied as sensitivity approach, whichever applicable.

The Multiple Imputation analysis will be carried out in three steps.

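### SAP Tables 6 and 11 count an early-exit DLQI score as a Week 16 or Week 44 result, so the two DLQI responder endpoints escape non-responder imputation and the as-observed summaries of the other scores are mislabelled

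*SAP*

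**What the plan says.** **Collection.** Protocol 5.6.1 says that DLQI and WLQ "are questionnaires self-administered by patients at Visits 2, 8 and EOT". The Flow Chart gives NAPSI, PPASI and PSSI the same schedule. Under Protocol 6.2.3.1, when a patient cannot or will not go on, "the patient should complete EOT Visit procedures instead of the next planned treatment period visit". An early leaver is therefore due all five instruments at exit.

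**Windows (SAP 6.0).** The general rule is: "In order to include all post baseline data, the first post-baseline interval starts on the first day after the first dose of study drug".
- Table 6, "Visit Windows for Other Efficacy Endpoints Only Collected at Week 16 in Part A (ITT_A Population", gives Rx Day 2 to 225 for Week 16, with the upper end limited by its footnote: "The minimum of upper bound and first dose date of study drug on or after Week 16".
- Table 11, "Visit Windows for Other Efficacy Endpoints Only Collected at Week 44 in Part B", gives Part B Rx Day 2 to 393 for Week 44, with no such limit.
- For PASI and sPGA, Table 4 gives Day 100 to 127 for Week 16, and Table 8 gives Part B Day 184 to 211 for Week 44.
- For repeated scores: "If more than one assessment is included in a time window the assessment closest to the nominal day will be used".

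**Missing data.** In SAP 10.1.4, "the NRI analysis will categorize any subject who has a missing value at a specific visit as a non-responder for that visit". NRI is primary for categorical variables. LOCF is primary for continuous variables, with as-observed analysis secondary. Exits for an adverse event of disease worsening are non-responders at later visits under NRI and MI. Protocol 7.5 also makes a binary endpoint with no later data a failure, and applies the same rules when a questionnaire has no data for a visit.

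**Endpoints (SAP 10.3.3).** DLQI has two responder endpoints (score 0 or 1; reduction of 5 or more points) and a change endpoint. WLQ, NAPSI, PPASI and PSSI have only change or percent-change endpoints.

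**The concern.** NRI acts only on a missing value. If the window starts the day after first dose and the instrument has one scheduled visit per Part, any exit score fills the endpoint visit and nothing is left to impute. The same patient at the same exit visit can then be a PASI 90 non-responder at Week 16 and a DLQI 0/1 responder at Week 16.

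Two things are at stake. The DLQI responder rates would not follow the missing-data rule that both documents state, and SAP 14.1 does not list this as a change from the protocol. The secondary analyses would also lose their purpose for these patients: NRI and LOCF give the same DLQI responder status, and LOCF and as-observed give the same continuous value.

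**Working it through.** **1. Reproduce the windows.**
- Single-visit tables: the lower bound is Rx Day 2. The upper bounds match a mirror image of the lower side: 113 + (113 − 1) = 225 and 197 + (197 − 1) = 393.
- PASI/sPGA, Week 16: midpoints (85 + 113)/2 = 99 and (113 + 141)/2 = 127 give 100 to 127.
- PASI/sPGA, Week 44: midpoints (169 + 197)/2 = 183 and (197 + 225)/2 = 211 give 184 to 211.

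All four match the printed tables. The tables put a midpoint day with the earlier visit, as the SAP's worked example does. The SAP's verbal rule would start each window one day earlier, which does not matter here.

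**2. Compare them.**

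| | PASI/sPGA | DLQI and the other four | Days labelled differently |
|---|---|---|---|
| Week 16 | 100–127 (28 days) | 2–225 (224 days) | 2–99 (98 days) |
| Week 44, Part B days | 184–211 (28 days) | 2–393 (392 days) | 2–183 (182 days) |

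**3. Follow one patient.** Suppose the exit visit is on Day 57, with no later assessment and a reason other than disease worsening.
- PASI and sPGA fall in the Week 8 window (44 to 71). Week 16 is missing, so NRI makes the patient a non-responder.
- DLQI falls in the Week 16 window. It is not missing, so NRI does not apply, and a score of 0 or 1 counts as a Week 16 response.
- WLQ, NAPSI, PPASI and PSSI get a Week 16 value equal to the exit value. LOCF is designed to give about the same. The as-observed analysis should exclude this patient but includes the exit score as on schedule.

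**4. Size for a DLQI responder endpoint.** The documents give neither an early-exit rate nor a DLQI response rate at exit, so both are assumed. Let d be the share of an arm whose only score in that Part is an exit score before the PASI window, and q the share of those who are DLQI responders at exit.

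Overstatement relative to NRI = d × q:
- low: 0.02 × 0.10 = 0.2 points, or 0.6 patients per 300
- middle: 0.05 × 0.30 = 1.5 points, or 4.5 per 300
- high: 0.10 × 0.60 = 6.0 points, or 18 per 300

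Shift in the risankizumab-minus-adalimumab difference, with the same q in both arms = q × (d for risankizumab − d for adalimumab):
- 0.10 × (0.02 − 0.05) = −0.3 points
- 0.30 × (0.05 − 0.10) = −1.5 points
- 0.60 × (0.02 − 0.10) = −4.8 points

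**5. Part B in patients.** The planned 120 re-randomised patients give about 60 per arm. With d of 10% and 5% and q of 30%, the extra responders are 60 × 0.10 × 0.30 = 1.8 and 60 × 0.05 × 0.30 = 0.9, a difference of about one patient.

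**The case against.** The windows follow a stated convention that aims to use all post-baseline data, and with one scheduled visit per Part a wide window is its natural result. The exposed group is also limited. Patients who stop drug are asked to stay for the remaining visits. A later score nearer the target day replaces the exit score. Table 6 is cut at the first dose on or after Week 16. Exits for disease worsening are already non-responders. The late ends of the windows matter little, because none of these instruments is scheduled at EOO. The affected endpoints are further endpoints, which Protocol 7.3.3 plans to summarise descriptively.

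All of this stands as a limit on size. None of it covers a patient who leaves early for another reason and has only the exit score. The SAP also does not say how the worsening rule treats a score taken at the exit visit itself. The descriptive-only argument is weaker than it looks, because SAP 10.1 provides treatment comparisons for efficacy variables in ITT_A and ITT_B_RR.

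A reader might infer that all five instruments escape NRI. They do not: four have no responder endpoint, and for them and for mean DLQI change the primary rule is LOCF, which the wide window roughly reproduces. A reader might also infer that the windows favour risankizumab. The documents do not support that: with equal response at exit, more exits on adalimumab would shrink the apparent benefit of risankizumab.

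**Conclusion.** The point holds in a limited form. For the two DLQI responder endpoints, Tables 6 and 11 override the primary NRI rule for patients whose only score in a Part is an early-exit score, unless the exit was for disease worsening. For DLQI change, WLQ, NAPSI, PPASI and PSSI, only the as-observed analysis is affected.

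The overstatement is about 0.2 to 6 points per arm. This rests wholly on the assumed 2%–10% early exit and 10%–60% response at exit. The effect on the treatment difference depends on d × q in each arm. With equal q and more exits on adalimumab it was −0.3 to −4.8 points in the cases tried, against risankizumab.

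The co-primary and ranked endpoints use the 28-day windows and are unaffected, and the DLQI endpoints lie outside the testing hierarchy. The correction is worth making because it is cheap and removes a conflict within the plan, but it does not bear on the trial's main claims.

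**What to change.** - In Table 6, raise the lower bound for Week 16 from Rx Day 2 to Rx Day 100. Keep 225 and the cap at the first Part B dose.
- In Table 11, raise the lower bound for Week 44 from Part B Rx Day 2 to Part B Rx Day 184. Keep 393.
- Add one sentence to SAP 10.1.4: for these instruments, a post-baseline score in the same Part before the window (early EOT) is used only as the carried-forward value in the LOCF analysis, and is treated as missing at Week 16 or Week 44 in the NRI and as-observed analyses.

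The sentence is needed because SAP LOCF carries forward from a previous visit, and after the change an early exit score would have no visit label. The upper bounds should not be cut to the PASI limits. Protocol 4.1.4 requires Visit 8 even after Day 126, so a Week 16 limit of 127 would discard genuine late scores and turn them into non-response.

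The cost is two table entries and one sentence. A few more patients will count as DLQI non-responders or drop out of the as-observed summaries.

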At Visit 5 (Week 4), Visit 8 (Week 16), Visit 9 (Week 20), Visit 11 (Week 28) and Visit 12 (Week 32) the patient self-administers BI 655066 (active or placebo) at the study site under supervision of study personnel. The two injections at these dosing visits should be administered within approximately 5 minutes. The study personnel will complete a study drug self-administration questionnaire for the BI 655066 (active or placebo) self-administrations by patients (refer to [Section 5.6.2](#) and [Appendix 10.8](#)).

BI 655066 (active and matching placebo) as well as adalimumab (active or matching placebo) will be administered as a subcutaneous injection in the abdomen (preferably lower abdomen) or thigh. The two BI 655066 (active or matching placebo) injections done subsequently within approximately 5 minutes should be at least 2 cm apart and should not be close to a vein. The injection sites should avoid sites of psoriasis involvement as well as sites where the skin is tender, bruised, erythematous, or indurated, and should be alternated to other areas for subsequent doses. Further information regarding injection details will be provided in the ISF. The dosing time to be entered in the eCRF is always the time of administration of the first syringe.

For study site visits, investigators and patients are instructed to adhere to the regular allowed time window according to the [Flow Chart](#) (i.e. ± 1 day at Visit 3; ± 3 days at Visits 4 to 14 and at EOT Visit; ± 7 days at EOO Visit). In the rare event that a patient comes too late to a scheduled visit it must be decided whether the delayed visit should still be performed or should be skipped. [Table 4.1.4: 1](#) shows the upper limits for extended time windows up to which study visits can still be performed

Table 4.1.4: 1 Upper Limits for extended time windows for study visits

Visit	Week	Scheduled Visit Day	Upper limit of delay (Days)	Upper limit (Day)
V3	Week 1	Day 8	+ 6	Day 14
V4	Week 3	Day 22	+ 6	Day 28
V5	Week 4	Day 29	+ 27	Day 56
V6	Week 8	Day 57	+ 27	Day 84
V7	Week 12	Day 85	+ 27	Day 112

Table 4.1.4: 1 Upper Limits for extended time windows for study visits (cont'd)

Visit	Week	Scheduled Visit Day	Upper limit of delay (Days)	Upper limit (Day)
V8*	Week 16	Day 113	+ 13	Day 126*
V9	Week 20	Day 141	+ 27	Day 168
V10	Week 24	Day 169	+ 27	Day 196
V11	Week 28	Day 197	+ 27	Day 224
V12	Week 32	Day 225	+ 27	Day 252
V13	Week 36	Day 253	+ 27	Day 280
V14	Week 40	Day 281	+ 27	Day 308

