Week 24	169	[156, 183]
Week 28	197	[184, 211]
Week 32	225	[212, 239]
Week 36	253	[240, 267]
Week 40	281	[268, 295]
Week 44	309	[296, 323]
Week 48 (EOT + 4 Weeks)	337	[324, 351 ^b]

Rx Day calculated relative to the first dose of risankizumab.

- a. If time is collected in vital signs, restrict to records prior to the first dose of risankizumab.
- b. The minimum of upper bound and 105 days of last dose of risankizumab for safety analyses.

Table 15. Visit Windows for Local Tolerability Parameters for ALL_RZB Population

Window Label	Target Day	Time Window
Week 1	8	[2, 15]
Week 3	22	[16, 25]
Week 4	29	[26, 71]
Week 16	113	[72, 155]
Week 28	197	[156, 253]
Week 44	309	[254, 323 ^a]

Rx Day calculated relative to the first dose of risankizumab.

- a. The minimum of upper bound and 105 days of last dose of risankizumab for safety analyses.

The time windows specified below will be used for the summary of study drug injections of each period.

Table 16. Visit Windows for Summary of RZB Injections for Part A

Window Label	Target Day	Time Window
Week 0	1	≤ 1
Week 4	29	[2, 57 ^a]

Rx Day calculated relative to the first dose of study drug.

a. Before the first dose on or after Week 16.

Table 17. Visit Windows for Summary of RZB Self-Administration Questionnaire in Part A

Window Label	Target Day	Time Window
Week 4	29	[2, 57 ^a]

Rx Day calculated relative to the first dose of study drug.

a. Before the first dose on or after Week 16.

Table 18. Visit Windows for Summary of RZB Injections for Part B and RZB Self-Administration Questionnaire

Window Label	Target Day	Time Window
Week 16	1	≤ 1
Week 20	29	[2, 57]
Week 28	85	[58, 99]
Week 32	113	[100, 127]

Rx Day calculated relative to the first dose of study drug in Part B.

Table 19. Visit Windows for Summary of ADA Injections for Part A

Window Label	Target Day	Time Window
Week 0	1	≤ 1
Week 1	8	[2, 15]
Week 3	22	[16, 29]
Week 5	36	[30, 43]
Week 7	50	[44, 57]
Week 9	64	[58, 71]
Week 11	78	[72, 85]
Week 13	92	[86, 99]
Week 15	106	[100, 113]

Rx Day calculated relative to the first dose of study drug.

Table 20. Visit Windows for Summary of ADA Injections for Part B

Window Label	Target Day	Time Window
Week 17	8	[1, 15]
Week 19	22	[16, 29]
Week 21	36	[30, 43]
Week 23	50	[44, 57]
Week 25	64	[58, 71]
Week 27	78	[72, 85]
Week 29	92	[86, 99]
Week 31	106	[100, 113]
Week 33	120	[114, 127]
Week 35	134	[128, 141]
Week 37	148	[142, 155]
Week 39	162	[156, 169]
Week 41	176	[170, 183]

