9.0 Study Drug Exposure and Compliance

Summary of study drug exposure will be provided for each treatment arm in each treatment part in the corresponding ITT populations. Study drug compliance will be summarized in ITT_A, ITT_B_RR populations.

Study drug exposure (days) will be summarized using the sample size, mean, standard deviation, minimum, median and maximum for each treatment part. In addition

cumulative exposure of RZB will be also summarized in the ALL_RZB Population.
Study drug exposure will be summarized as follows:

Study Drug Exposure (in Days) in Each Part:

Part A:

- For subjects who did not continue into Part B:
 - Date of last injection in Part A – Date of first injection in Part A + 14 days (ADA)
 - Date of last injection in Part A – Date of first injection in Part A + 84 days (RZB)
- For subjects who continued into Part B: the minimum of
 - Date of first injection in Part B – Date of first injection in Part A.
 - Date of last injection in Part A – Date of first injection in Part A + 14 days (ADA)
 - Date of last injection in Part A – Date of first injection in Part A + 84 days (RZB)

Part B:

- Date of last injection in Part B – Date of first injection in Part B + 14 days (ADA)
- Date of last injection in Part B – Date of first injection in Part B + 84 days (RZB)

ALL_RZB:

For study drug exposure during the administration of risankizumab in the ALL_RZB Population:

- Date of last injection of risankizumab – Date of first injection of risankizumab + 84 days.

Compliance

There will be a summary of the number of subjects receiving study drug and dose at each scheduled study drug administration time point for adalimumab and for risankizumab, separately. This will be repeated on the cumulative number of doses.

When computing compliance at each scheduled time point, the denominator for each week will include all subjects in each analysis population who have not prematurely discontinued study drug (or prematurely discontinued from study) prior to the scheduled study drug injection.

Self-Administration of Risankizumab Questionnaire

There will be a summary of the self-administration of risankizumab questionnaire completed by supervising nurse/health care professional.

The following items will be summarized as-observed at each visit:

- Patient able to inject all of the liquid (Yes/No)

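### SAP Table 18 closes its Week 28 and Week 32 injection windows before the protocol's extended visit limits, so a very late risankizumab or placebo injection is mislabelled or falls in no window

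*SAP*

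**What the plan says.** **SAP 6.0, Table 18** windows both the Part B risankizumab injections (active or dummy) and the self-administration questionnaire. The introduction to the injection tables reads: "The time windows specified below will be used for the summary of study drug injections of each period". The Week 28 row is "Week 28 85 [58, 99" (target Rx Day 85, window 58 to 99). The Week 32 row, the last in the table, is "Week 32 113 [100, 127" (target 113, window 100 to 127). The day count is set by the footnote: "Rx Day calculated relative to the first dose of study drug in Part B".

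**Protocol 4.1.4, Table 4.1.4: 1** "shows the upper limits for extended time windows up to which study visits can still be performed". For Visit 11 (Week 28) it gives "Day 197 + 27 Day 224" and for Visit 12 (Week 32) "Day 225 + 27 Day 252". The text around the table sets the regular window at ±3 days, treats a late visit as a rare event, and leaves it to be decided whether such a visit is performed or skipped. Protocol 6.1 counts every visit from Day 1, so a late Visit 8 does not move Visits 11 and 12.

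**SAP 9.0** plans a "summary of the number of subjects receiving study drug and dose at each scheduled study drug administration time point", repeated on the cumulative number of doses. Its denominator keeps every patient who has not stopped study drug or left the study before the scheduled injection.

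**The concern.** The protocol accepts injections on days that the SAP's table either gives to another visit or does not cover. The SAP has no rule for an injection outside every window. The nearest-to-nominal-day rule in SAP 6.0 is stated for efficacy, tolerability, laboratory and vital-sign data, and it chooses only among records inside one window.

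The label carries information. Under Protocol Table 4.1.4: 2, a patient switched from adalimumab to risankizumab receives placebo at Week 28 and active drug at Week 32. At stake is whether the by-visit compliance table for the re-randomised patients, and the questionnaire summary, show correctly which scheduled injections were given.

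**Working it through.** **Inputs.** Table 18 windows (SAP 6.0): Week 20 = 2 to 57, Week 28 = 58 to 99, Week 32 = 100 to 127. Protocol limits (Table 4.1.4: 1): Visit 8 Day 126, Visit 9 (Week 20) Day 168, Visit 11 Day 224, Visit 12 Day 252. Visit 8 may be as early as Day 110 (113 − 3). The first Part B dose is taken to be on the day of Visit 8.

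**Formula.** Rx Day = study day − Visit 8 day + 1.

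**Reproducing the plan's figures, Visit 8 on Day 113.**
- Targets: 197 − 113 + 1 = 85 and 225 − 113 + 1 = 113, as in Table 18.
- Upper bounds: (29 + 85)/2 = 57, (85 + 113)/2 = 99 and 113 + 14 = 127, as in Table 18.
- Protocol limits: 197 + 27 = 224 and 225 + 27 = 252.

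**Protocol limits against the windows, Visit 8 on Day 113.**
- Week 28 limit: 224 − 113 + 1 = Rx 112, which is 13 days past 99. Days 212-224 (Rx 100-112) are labelled Week 32.
- Week 32 limit: 252 − 113 + 1 = Rx 140, which is 13 days past 127. Days 240-252 (Rx 128-140) are in no window.
- Week 20 limit: 168 − 113 + 1 = Rx 56, inside 2 to 57.

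**Dependence on the Visit 8 day.** The shortfall is (224 − V8 + 1) − 99 = 126 − V8 for Week 28, and (252 − V8 + 1) − 127 = 126 − V8 for Week 32.

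| Visit 8 day | Week 28 days labelled Week 32 | Week 32 days in no window | Shortfall (days) |
|---|---|---|---|
| 110 | 209-224 | 237-252 | 16 |
| 113 | 212-224 | 240-252 | 13 |
| 116 | 215-224 | 243-252 | 10 |
| 120 | 219-224 | 247-252 | 6 |
| 125 | 224 | 252 | 1 |
| 126 | none | none | 0 |

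**How late a visit must be.** The first affected day is V8 + 99 for Week 28 and V8 + 127 for Week 32. Subtracting 197 and 225, both are V8 − 98 days late: 12 days for Visit 8 on Day 110, 15 for Day 113, 18 for Day 116.

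**Effects on other rows.** With Visit 8 on Day 110, a Week 20 dose on Days 167-168 is Rx 58-59 and is labelled Week 28. With Visit 8 itself very late, on Day 126, a Week 32 dose on Days 222-224 is Rx 97-99 and is also labelled Week 28.

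**Can a better cut-off solve it?** No. A late Week 28 visit may run to Day 224, and an on-time Week 32 visit may start on Day 222 (225 − 3). The ranges overlap, so no single day separates them.

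**Number of patients.** The documents give no share of visits this late. If it were 0.5% to 2% (an assumption), then of 120 re-randomised patients 0.6 to 2.4 would be affected per visit. In the risankizumab arm alone, about 60 patients, it would be 0.3 to 1.2.

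**The case against.** The strongest reply is that almost nothing happens. The regular window is ±3 days, and with Visit 8 on Day 113 every Week 20, 28 or 32 visit inside it is filed correctly. Table 4.1.4: 1 is a tolerance for exceptional cases. Table 18 feeds descriptive summaries only: the Week 44 PASI analysis uses Table 8, and exposure in SAP 9.0 uses injection dates. The 75% rule for the Part B per-protocol population (SAP 5.1) does not say that it counts by these windows, and losing one of four risankizumab visits gives 3/4 = 75%, which still passes. All of this stands and sets the size of the point.

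Two stronger readings are tempting and go too far.

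- A reader might infer that a late placebo pair will be shown as the active Week 32 dose. That also requires the Week 32 injection to be missed or given after Rx Day 127. If Week 32 is given on time, both injections fall in 100 to 127: Week 32 is correctly shown as received and it is Week 28 that looks missed. SAP 9.0 also summarises drug and dose, so it is not established that placebo would be counted as active.
- A reader might infer that the SAP reports a permitted active dose as not given. It says no such thing. This is a probable consequence of a dose with no window and a patient who stays in the denominator.

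A timing-based table also has some merit, because it shows that a dose was off schedule. Table 18 does not do this well: it gives the dose another visit's label or drops it, without marking it late.

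**Conclusion.** The point holds as a minor inconsistency. Table 18 and Protocol Table 4.1.4: 1 disagree for any Visit 8 from Day 110 to Day 125, by 126 minus the Visit 8 day, and no other SAP rule recovers the affected injections. The mislabelling is not strictly confined to the Week 28 and Week 32 rows, since an early Visit 8 also exposes Week 20.

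The reach is small: visits about two weeks or more off schedule, plausibly zero to two re-randomised patients per visit, in the by-visit compliance and questionnaire summaries. The cumulative dose count is affected only if it uses these windows, which is not stated. The documents do not support a claim that the Week 44 comparison is biased or that exposure is misreported. The patient count rests on an assumed share of late visits; the day arithmetic rests only on the two tables and on the first Part B dose falling on the day of Visit 8.

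**What to change.** In SAP 6.0, assign Part B risankizumab injections and questionnaires to Weeks 16, 20, 28 and 32 by scheduled visit (Visits 8, 9, 11 and 12) or by IRT medication number. Protocol 4.1.4 ties these injections to those visits and has medication numbers entered in the eCRF. It does not say that a visit number is stored with each administration, so confirm this before programming.

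Use the Table 18 day windows only as a fallback for records that cannot be linked, and leave the Week 32 window open to the end of Part B. No later risankizumab injection is scheduled, so nothing is gained by closing it. A fixed bound such as Rx Day 140 would fit only Visit 8 on Day 113; Day 110 would need 252 − 110 + 1 = 143. State how an injection outside every window is shown.

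The cost is a table footnote and a programming rule, ideally before database lock. There is one small downside: filing by visit hides lateness. List or flag the actual Rx Day of any dose given outside the regular ±3 days.
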